3.4. Study Procedures

Please refer to Section 8.0 of the study protocol for details regarding the study procedures.

3.5. Unmasking

This is an open-label study; blinding is not applicable.

4. POPULATIONS DEFINITIONS

The following analysis sets will be evaluated and used for presentation and analysis of the data.

Analysis sets defined by eye will be respect to each eye. For example, the Safety Analysis Set for the CE will be determined by measurements taken on the CE. The subject-level analysis sets consist of subjects who meet the criteria in at least one of the eye-level analysis sets.

Screening Analysis Set: Includes all subjects who signed the informed consent form.

Safety Analysis Set (SAF): Includes all subjects/eyes who received at least one dose of study drug in Helia in either eye. Subjects/eyes will be analyzed according to their actual treatment. The SAF will be defined at the subject level or the eye level, depending on whether the endpoint is to be analyzed at the subject level or the eye level.

The disposition data will be presented for all screened subjects. The SAF will be the primary set for the analysis of the safety parameters. The SAF will also be used for descriptive summaries of demographics, baseline characteristics, and ocular/non-ocular medical history.

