Duration of Subject Participation:	Until provision of continued treatment by other means is available, provided the subject's benefit-risk assessment remains positive. Subject participation is expected to be 12 months for subjects who will only receive follow up in this study (i.e., chosen not to have any treatment administered).			
Rationale:	in exon 13 of the USH2A gene, and disease management is supportive; therefore, significant unmet medical need exists in this sight-threatening condition. QR-421a is designed to target mutations in exon 13 of USH2A gene specifically. Hybridization of QR-421a to the pre-messenger ribonucleic acid (pre-mRNA) molecule modulates the ribonucleic acid (RNA) splicing process, which leads to exclusion of exon 13 from the mRNA. The exclusion of exon 13 results in the production of a functional (shorter) usherin protein. It is hypothesized that the production of usherin protein restores the outer segments of the photoreceptors at prevents their degeneration.		nent is supportive; therefore, a reatening condition. of USH2A gene specifically. nucleic acid (pre-mRNA) sing process, which leads to a of exon 13 results in the t is hypothesized that the ents of the photoreceptors and Subjects that have participated a-001, will be given the	
			lerability, and efficacy data of	
Objectives:		Endpoints:		
Primary		Primary endpoints		
To evaluate long-term safe QR-421a	ty and tolerability of	Incidence and severityIncidence and severity	of ocular adverse events (AEs) of non-ocular AEs	
Secondary		Secondary endpoints		
To evaluate long-term efficient	eacy of QR-421a	Change from baseline in the following outcome measures:		

Page 4 of 65 24 May 2022 **ProQR Therapeutics**

To evaluate long-term systemic exposure of QR-421a Exploratory		 Best Corrected Visual Acuity (BCVA) Low Luminance Visual Acuity (LLVA) Ellipsoid Zone (EZ) area/width by spectral domain optical coherence tomography (SD-OCT) Static perimetry Microperimetry Exposure of QR-421a in serum Exploratory efficacy endpoints	
Number of Subjects (planned):		s is dependent on the number of eligible subjects that have ng clinical studies with QR-421a, including 20 subjects 01.	

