To address the potential risks defined in the toxicology studies, the reported risks from oligonucleotides administered by IVT injection, and the risks associated with the IVT injection procedure, extensive monitoring to protect subject safety is incorporated in this study and will include assessments of subjects' ophthalmic function and anatomy, in particular, monitoring of anterior, intermediate and posterior segment inflammation by slit-lamp biomicroscopy, clinical lens grading using the Age-Related Eye Diseases Study (AREDS) Clinical Lens Grading

ProQR Therapeutics Page 19 of 65 System, monitoring for retinal changes by OCT, and VF testing to monitor changes in retinal sensitivity. This extensive clinical monitoring provides a means to allow early detection and/or prevention of potential AEs such as early signs of macular edema appearance or worsening, decrease in BCVA, the elevation of IOP, intraocular inflammation, lens opacities, and retinal structural modifications. In addition, the visit schedule is designed to monitor subjects one day following IVT injection and a second time within 1 week of IVT injection to monitor for signs of endophthalmitis and intraocular inflammation, consistent with guidelines for IVT injections (Avery 2014).

ProQR Therapeutics Page 20 of 65 24 May 2022

Detailed information about benefits and potential risks of QR-421a, as well as information on nucleotide AONs as a class of therapeutics can be found in the IB.

2.4 **Study Rationale**

There are currently no approved therapies for the treatment of RP due to mutations in exon 13 of the USH2A gene and disease management is supportive; therefore, an important unmet medical need exists in this condition.

Available safety and efficacy data from study PQ-421a-001 support the therapeutic potential observed in the nonclinical studies and warrant the initiation of the additional clinical studies to confirm benefit-risk.

This extension study allows subjects having participated in QR-421a clinical studies, including study PQ-421a-001, to continue to receive treatment, or follow up, and to observe the long-term safety, tolerability, systemic exposure, and efficacy of treatment with QR-421a. Additionally, this extension study allows for the treatment of the previously untreated fellow/contralateral eye for subjects from study PO-421a-001.

2.5 **Dose Selection**

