2. INTRODUCTION AND STUDY OBJECTIVES

2.1. Introduction

Study PQ-421a-002 (Helia) aimed to evaluate the safety, tolerability, and efficacy of ultevursen in subjects with Retinitis Pigmentosa (RP) due to mutations in exon 13 of the *USH2A* gene. This open-label, extension study allowed subjects who have participated in ultevursen clinical studies to continue to receive treatment or follow up, and to observe the long-term safety, tolerability, systemic exposure, and efficacy. This open-label extension study also allowed for treatment of the previously untreated contralateral eye (CE; if applicable).

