5.6. Safety – Adverse events

A treatment-emergent AE (TEAE) is defined as an event that was not present prior to administration of the dose of study drug (ultevursen or sham-procedure) and present after the dose or if it represents the exacerbation of an event that was present prior to the dose.

Adverse events will be summarized by treatment group separately as follows:

- For non-ocular AE:
 - by subject, therefore, in any tabulation, a subject contributes only once to the count for a given adverse event (System Organ Class [SOC] or Preferred Term [PT]); and
 - During the overall study period (i.e., up to the last visit for the last subject).
 - Time to onset will be calculated in hours, relative to the last dose received, irrespective of which eye received the last dose (i.e., TE or CE).
- For ocular AE:

- by eye frequencies, separately for the TE and the CE, therefore, in any tabulation, an eye contributes only once to the count for a given AE (by SOC or PT). AEs that are reported in both eyes (i.e., OU) will be reported individually by eye in the tabular summaries; and
- During the overall study period (i.e., up to the last visit for the last subject).
- Time to onset will be calculated in hours, relative to the last dose received in the eye experiencing the ocular AE.

Unless otherwise stated, any summary of any type of TEAEs which includes the SOC and PT of the events will order the SOC and the PTs within the SOC by descending incidence of PT.

The following summary tables will be produced separately according to the type of AEs (ocular/non-ocular where applicable) as defined above:

- Overview of Ocular Adverse Events for Treatment Eye during the overall study period (Safety Population)
- Overview of Ocular Adverse Events for Contralateral Eye during the overall study period (Safety Population)
- Overview of Non-Ocular Adverse Events during the overall study period (Safety Population)
- Summary of Ocular Treatment-Emergent Adverse Events for Treatment Eye during the overall study period by MedDRA System Organ Class and Preferred Term (Safety Population)
- Summary of Ocular Treatment-Emergent Adverse Events for Contralateral Eye during the overall study period by MedDRA System Organ Class and Preferred Term (Safety Population).
- Summary of Non-Ocular Treatment-Emergent Adverse Events during the overall study period by MedDRA System Organ Class and Preferred Term (Safety Population).
- SAEs
- AESIs

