5.7. Other Data Listings to be Generated

The following by-subject data listings for the Safety Population will be provided:

- Subject Disposition
- Screen Failures (All Screened Subjects)
- Demographic and Baseline Characteristics (Safety Population)
- Non-Ocular Medical History (Safety Population)
- Ocular Medical History (Safety Population)
- Study Drug Administration of the TE (Safety Population)
- Study Drug Administration of the CE (Safety Population)
- BCVA Based on ETDRS (Safety Population)
- Low Luminance Visual Acuity (LLVA) (Safety Population)
- Spectral Domain Optical Coherence Tomography (SD-OCT) (Safety Population)
- Static Perimetry (Safety Population)
- Microperimetry (Safety Population)
- Ophthalmic exam (Safety Population)

- Non-Ocular Adverse Events (Safety Population)
- Ocular Adverse Events (Safety Population)
- Prior and/or Concomitant Medications (Safety Population)
- Laboratory results: Hematology, Coagulation, Chemistry and Urinalysis (Safety Population)

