6. CHANGES TO PLANNED ANALYSES

As the study is prematurely stopped by Sponsor's decision, no formal statistical analysis will be produced. Only disposition, demographic and baseline characteristics, and overview of AEs will be summarized in tables. By-subjects data listings will be produced based on raw data.

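### AEs collected in Helia from follow-up-only subjects who had active QR-421a earlier appear in neither the AE overview tables nor the AE listings (SAP 4, 5.6, 5.7)

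*SAP*

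**What the plan says.** Both documents present follow-up without dosing as part of the study. SAP 2.1 says that the study "allowed subjects who have participated in ultevursen clinical studies to continue to receive treatment or follow up, and to observe the long-term safety", and protocol 2.4 says much the same. The protocol synopsis adds: "Subject participation is expected to be 12 months for subjects who will only receive follow up in this study". Protocol 4.2.1.2 plans 6-monthly visits for them. Protocol 8.1 has AE information recorded over the whole study, and 4.1.1 makes incidence and severity of ocular and non-ocular AEs the primary endpoints.

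SAP 4 defines the Safety Analysis Set in these words: "Includes all subjects/eyes who received at least one dose of study drug in Helia in either eye". It makes this the main set for safety. Disposition is handled differently: "The disposition data will be presented for all screened subjects".

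SAP 5.6 attaches the set to the AE overviews, for example "Overview of Non-Ocular Adverse Events during the overall study period (Safety Population)". SAP 5.7 opens with "The following by-subject data listings for the Safety Population will be provided", and both the ocular and the non-ocular AE listing repeat that label. SAP 6, written for the early stop, cuts the tables to disposition, demographics and baseline, and the AE overview. On listings it says only: "By-subjects data listings will be produced based on raw data".

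**The concern.** A subject who received active QR-421a in a preceding study and then enters Helia for follow-up alone is observed for long-term safety, which is the purpose of the extension. Whatever AEs the sites record for that subject have no stated place in the AE overviews or listings.

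The protocol itself does not treat such a subject as unexposed. Section 2.5 omits the loading dose in study eyes previously given 200 µg, to allow for drug still present from the earlier injection. Section 6.2.2 requires contraception for up to 24 months after the last dose. The group may also be selected. Protocol 4.2 makes dosing conditional on a positive benefit-risk assessment and offers follow-up as the alternative, although the synopsis shows that follow-up alone can also simply be the subject's choice.

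With the reporting reduced by SAP 6, the AE listings become the main record of the primary endpoint. For non-serious events that are not of special interest, a reader of the report could not tell whether none occurred in these subjects or whether they were not shown.

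**Working it through.** There is no planned figure to reproduce. The check is to follow one subject through the rules and then count the outputs affected.

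**The subject.** Active QR-421a in PQ-421a-001, no injection in Helia, about 12 months of follow-up, one non-serious AE recorded in Helia.

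1. Collection: protocol 8.1 covers the event. Section 9.3.1 classes events arising before the first dose of study treatment as non-treatment-emergent. It does not expressly address a subject who never has a first dose, but that is the natural extension.
2. Disposition: the subject counts, because all screened subjects are included (SAP 4).
3. Safety Analysis Set: the subject is out, because no eye was dosed in Helia. The phrase about either eye is ambiguous for the undosed eye of a dosed subject, but it makes no difference here.
4. AE outputs named in SAP 5.6 and 5.7:

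| Output | Number | Population label | Is the event shown? |
|---|---|---|---|
| AE overviews (TE, CE, non-ocular) | 3 | Safety | No, because of the set definition |
| TEAE summaries by SOC and PT | 3 | Safety | No, and not under the TEAE definition either |
| SAEs, AESIs | 2 | None | Open (and only if the event qualifies) |
| AE listings (ocular, non-ocular) | 2 | Safety | No, because of the set definition |

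Total 3 + 3 + 2 + 2 = 10 outputs. Eight carry the label (3 + 3 + 2). The set definition decides at most 3 + 2 = 5 of them. It is at most five because the overview shells are in a separate document (SAP 8). If those shells count only TEAEs, the overviews would omit the event in any case and two listings remain.

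5. Does SAP 6 repair this? Its phrase about raw data describes the source of the listings, not who is in them. SAP 5.7 names a wider set where it wants one, for screen failures, and does not do so for AEs.

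**How many subjects.** Neither document says. From PQ-421a-001 it must be fewer than 20, because that study had 20 subjects and a sham control (protocol 2.2.2 and 2.5). The number from any other preceding study is not stated.

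**Illustration, all inputs assumed.** With k such subjects and independent per-subject risk p of a given AE, the chance that at least one has it is 1 − (1 − p)^k.
- k = 0: the chance is 0.
- k = 1: 0.05, 0.10 and 0.20 for p = 5%, 10% and 20%.
- k = 5: 1 − 0.95^5 = 0.23, 1 − 0.90^5 = 0.41 and 1 − 0.80^5 = 0.67.

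So even a handful of subjects could plausibly contribute an event that these outputs do not show.

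**The case against.** The strongest reply is that a safety set of subjects dosed in the study is normal practice. Protocol 9.0 ties safety assessment to subjects who receive study treatment, and the SAP 3.2 and 3.3 groups are defined by Helia regimen, with no column for the undosed. The study was also stopped early, and the SAP supports only an abbreviated report. All of this stands. It is a reason to leave the set alone, but not a reason to leave recorded AEs without any listing.

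Four stronger readings are tempting, and the documents do not support them.

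- *The set definition removes these events from all eight labelled outputs.* Three of the eight are TEAE summaries, which would omit the events whatever the population.
- *The SAP contradicts the protocol's safety population.* Protocol 10.5 refers to receipt of any QR-421a and could take in doses from a preceding study. Read with 9.0, it can equally mean receipt in this study. No firm conflict can be claimed.
- *Serious events are hidden.* Protocol 9.4 sends every SAE to the sponsor within 24 hours. That is not the same as tabulation, but the SAE and AESI tables have no label and may include these subjects. Because SAP 4 makes the Safety Analysis Set the main one for safety, their inclusion is not assured either.
- *Reported AE incidence is biased in a known direction.* The number of subjects and of their events is unknown, and adding them would change numerator and denominator together.

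It is also fair to say that AE capture for a never-dosed subject rests on 8.1 and on an extension of 9.3.1, and that 9.3.1 sends AEs continuing from the preceding study to medical history. The point therefore concerns events that were in fact recorded as AEs in Helia.

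**Conclusion.** The point holds in limited form. Followed literally, SAP 4, 5.6 and 5.7 leave AEs of previously active-dosed, follow-up-only subjects out of both AE listings and, unless the overviews are confined to TEAEs, out of three overview tables as well: at most five of ten AE outputs. The data belong to the primary endpoint and are meant to be collected. The reading of the set definition is secure. The practical consequence is uncertain, because the number of subjects may be zero and the output shells were not available. The conclusion assumes that at least one such subject enrolled, that AEs were recorded for that subject, and that the shells do not already widen the population. It does not extend to subjects who had only sham before. This is a cheap improvement to make before the outputs are run. It is not a reason to doubt the dosed-subject results.

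**What to change.** Keep the Safety Analysis Set, the TEAE definition and all existing tables. Add to SAP 5.6 and 5.7:

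- One separate AE listing and one short overview for enrolled subjects who were given active QR-421a in a preceding study and received no dose in Helia. Include non-treatment-emergent AEs, count ocular events by eye and non-ocular events by subject, and use the number of such eyes or subjects as the denominator.
- A stated population for the SAE and AESI outputs, run so that these subjects are included or shown separately.
- If there are no such subjects, one sentence in the report saying so, in place of the listing and overview.

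The cost is one listing, one small table and a flag for active treatment in the preceding study. No new data collection is needed. The drawback is a table with a very small denominator, so it should show counts and leave interpretation to the listing.

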5. STATISTICAL METHODS

5.1. Computing Environment

All information and analyses in the tables and listings provided will be performed using SAS statistical software Version 9.4 or later, unless otherwise noted. The Medical History (MH) and Adverse Events (AEs) will be coded using Medical Dictionary for Regulatory Activities (MedDRA) version 24.1. The Prior and Concomitant Medications will be coded using World Health Organization (WHO) Drug version Global B3 September 2021.

5.2. Definition of Baseline

Baseline is defined as the data most recently collected prior to the administration of study treatment.

5.3. Data Handling

5.3.1. General

Unless otherwise noted, the data reported in the listings will be as reported on the electronic case report form.

5.4. General Statistical Methods

All output will be incorporated into Rich Text Format (RTF) files and bookmarked PDFs, sorted and labeled according to the International Conference on Harmonisation (ICH) recommendations, and formatted to the appropriate page size(s).

Tabulations will be produced for appropriate disposition and demographic characteristics.

For measurements of continuous variables, summary statistics of absolute values will be reported and will include n, mean, standard deviation, median, and minimum and maximum values. The number of missing values will be displayed in parenthesis next to 'n'. Mean, standard deviation, median, will be presented with one more decimal place compared to the raw data, and minimum and maximum will be presented with the same number of decimal places as the raw data.

For categorical variables, summary tabulations of the number and percentage within each category of the parameter will be presented (as well as the number for missing data).

Denominator for percentages is column N. Percentages will be rounded to one decimal place. Therefore, there may be cases where for instance the total of the percentages does not exactly equal 100%.

Where appropriate, data will be listed by eye (i.e., TE, CE).

In summary tables the study treatments will be presented in the following order: 'Ultевурсен 180/60 µg', 'Ultевурсен 60/60 µg', and 'All Subjects'.

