4.0 STUDY OVERVIEW

4.1 **Criteria for Evaluation**

4.1.1 **Primary Endpoints**

- Incidence and severity of ocular adverse events (AEs)
- Incidence and severity of non-ocular AEs

4.1.2 **Secondary Endpoints**

- Change from baseline in the following outcome measures:
 - o Best Corrected Visual Acuity (BCVA)

ProQR Therapeutics Page 23 of 65

- Low Luminance Visual Acuity (LLVA)
- Static perimetry
- Ellipsoid Zone (EZ) area/width by spectral domain optical coherence tomography (SD-OCT)
- Microperimetry
- Exposure of QR-421a in serum

4.1.3 **Exploratory Endpoints**

4.2 **Study Design**

PQ-421a-002 is an open-label, extension study to evaluate the safety, tolerability, and efficacy of QR-421a in subjects with RP due to mutations in exon 13 of the USH2A gene.

Subjects that have participated in preceding QR-421a clinical studies, including study PQ-421a-001, will be given the opportunity to enroll into this extension study for continued dosing, provided the subject's benefit-risk assessment is positive, or for additional follow up. The Investigator, in consultation and agreement with the Medical Monitor, will decide on subject's enrollment upon assessment of subject's benefit-risk.

QR-421a will be first administered to the fellow eye and will be repeated every 6-month. Treatment of the study eye can commence as outlined in Section 6.1.5 and on the participant and when they completed their participation in the previous QR-421a study. The Investigator, in consultation and agreement with the Medical Monitor, will decide on dosing of both eyes. Continued subject treatment in this study will be pursued provided that the benefitrisk is positive for the individual subject, as discussed and agreed upon with the Medical Monitor.

The Sponsor, in consultation with the Investigator, may decide to modify the dose, the dosing interval for repeat injections in one eye or both eyes, hold the dose (delay or skip), or discontinue study drug for an individual subject, based on emerging safety and efficacy data and if it is anticipated to be in the best interest of the subject.

The same safety monitoring protocol and efficacy assessments will apply to both eyes.

ProQR Therapeutics Page 24 of 65

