5.6.1. Partial and Missing Date/Time for Adverse Events

Imputation of missing/partial AE date/time will be done only to identify TEAEs.

AE onset dates

- Partially missing onset date/time will be imputed as follows:

- When only Day is missing:
 - If Month & Year of the onset date are the same as Month & Year of the first administration date, the imputed onset date will be imputed as the minimum of the first administration date/time and the AE resolution date (imputed if needed).
 - Otherwise, the missing day will be replaced by “1.”
- When Day & Month are missing:
 - If Year of the onset date is the same as Year of the first administration date, the imputed onset date will be imputed as the minimum of the first administration date/time and the AE end date (imputed if needed).
 - Otherwise, the missing Day & Month will be replaced by “01 JAN.”
- If a partial AE start date is consistent with the actual start date being on Day 1, and either the AE end date information is completely missing, or the complete or imputed AE end date/time information indicates that the AE did not end before Day 1, the imputed AE start date will be Day 1 in the following scenarios:
 - The AE start time is missing (the AE will be flagged as treatment-emergent following the first dose of study treatment)
 - The AE start time is after the date/time of first dosing of study treatment on Day 1 (the AE will be flagged as treatment-emergent following the first dose of study treatment)
 - The AE start time is before the time of first dosing of study treatment on Day 1, and imputing the AE start date as Day 2 instead of Day 1 would be inconsistent with the partially recorded AE start date (e.g., the calendar month for Day 2 is not the same as for Day 1), or with the complete or imputed AE end date/time (in this case, the AE will not be flagged as treatment-emergent following the first dose of study treatment).
- Missing start time will be imputed with the time of administration if the day of AE start date and administration are identical, or with 00:00 otherwise.
- Completely missing onset dates for AEs will be imputed by the first administration date and the AE will be considered as treatment-emergent unless the end date/time of the AE (imputed if needed) or the end year of the AE (if day and month are missing) is entered and is before the first administration date. If the end date/time is before the first administration date, the AE will not be considered as treatment-emergent.

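### The treatment-emergent flag runs from the subject's first Helia dose, so treated-eye events up to 9 months before that eye's own dose count under its Helia regimen

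*SAP*

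**What the plan says.** **Endpoint and tables.** Protocol 4.1.1 makes the incidence and severity of ocular AEs a primary endpoint. SAP 5.6 counts them by eye, in separate TE and CE tables, over the overall study period. SAP 5.4 fixes the percentage base: "Denominator for percentages is column N". SAP 3.2 groups each eye by the regimen it received in Helia, plus a column for all eyes.

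**Dosing start.** Protocol 7.2 doses the fellow eye (the CE) from Day 1, and the study eye (the TE) from Month 3 or Month 9, depending on the participant.

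**Treatment-emergent flag.** The SAP 5.6 definition does not name an eye. It refers to "administration of the dose of study drug (ultevursen or sham-procedure) and present after the dose". The rules that apply it point to the subject. Protocol 9.3.1 classes events before the first study dose as non-treatment-emergent and captures as AEs those noted once the subject has been dosed. SAP 5.6.1 flags an event as treatment-emergent when "The AE start time is after the date/time of first dosing of study treatment on Day 1", and adds: "Completely missing onset dates for AEs will be imputed by the first administration date".

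**Time to onset.** This separate variable is counted by eye for ocular AEs: "relative to the last dose received in the eye experiencing the ocular AE".

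**Safety set.** SAP 4 says that "the Safety Analysis Set for the CE will be determined by measurements taken on the CE", but then defines membership, for subjects and eyes alike, by a Helia dose in either eye.

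**Exposure.** SAP 5.5.1 counts subjects dosed in each eye, and SAP 5.7 lists dosing by eye. No summary in the SAP text gives time at risk or number of injections.

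**The concern.** The counting unit is the eye, but the clock that makes an event treatment-emergent belongs to the subject. By plan it starts with an injection into the other eye. A TE event in Month 5, in an eye first dosed in Helia at Month 9, would be flagged treatment-emergent and shown under that eye's Helia regimen. SAP 5.6 shows the mismatch itself: that event has no earlier Helia dose in its own eye from which to count time to onset.

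At stake is what a reader takes the TE table to mean. It appears to describe eyes after Helia dosing, yet part of its numerator can precede that dosing. If the programmers use an own-eye clock instead, the TE and CE percentages rest on different lengths of follow-up and nothing in the table shows it.

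**Working it through.** The plan gives no AE rate or exposure figure to reproduce, so the check compares the two clocks under stated assumptions.

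**Inputs**
- First Helia dose: CE at month 0, TE at month 3 or 9 (Protocol 7.2).
- Window T: 12, 18 and 24 months are assumed, because the study stopped early (SAP 6) and the actual follow-up is not given. The planned 36 months is 24 months of treatment (Protocol synopsis) plus 12 months from the last dose to the end-of-study visit (Protocol 7.3), taking a last dose at Month 24.
- Event rate λ: assumed 0.5 per eye-year, constant, and equal in both eyes before and after dosing. A range of 0.25 to 1.0 is also shown.

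**Formulas**, with s the month of the TE's first dose
- Incidence over t months: 1 − exp(−λt/12).
- Part of the subject-clock window before the TE's own dose: s/T.
- Share of flagged TEs whose first event precedes their own dose: (1 − exp(−λs/12)) / (1 − exp(−λT/12)).

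**Results for a Month-9 TE, λ = 0.5**

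| T (months) | Pre-dose part of window | TE incidence, subject clock | Share with first event before own dose | Own-eye clock: CE vs TE months | Own-eye clock: CE vs TE incidence |
|---|---|---|---|---|---|
| 12 | 75% | 39.3% | 79.5% | 12 vs 3 | 39.3% vs 11.8% |
| 18 | 50% | 52.8% | 59.3% | 18 vs 9 | 52.8% vs 31.3% |
| 24 | 37.5% | 63.2% | 49.5% | 24 vs 15 | 63.2% vs 46.5% |
| 36 | 25% | 77.7% | 40.3% | 36 vs 27 | 77.7% vs 67.5% |

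Worked for T = 18: 1 − exp(−0.375) = 0.313 and 1 − exp(−0.75) = 0.528, so the share is 0.313/0.528 = 59%. With an assumed 20 Month-9 TEs, about 10.6 would be flagged, about 6.3 of them first before their own dose.

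**Range.** For λ from 0.25 to 1.0 the share runs from 54.7% to 67.9% at 18 months and from 32.4% to 55.5% at 36 months. For a Month-3 TE at λ = 0.5 it is 0.1175/0.528 = 22.3% at 18 months and 0.1175/0.777 = 15.1% at 36 months.

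**Reading.** The share is not the amount by which the printed figure is inflated, because some of these eyes would also have an event after their own dose. At 18 months the printed TE incidence is 52.8% on the subject clock and 31.3% on the own-eye clock. On the own-eye clock, equal rates in the two eyes print as 52.8% and 31.3%, purely because of 18 versus 9 months.

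**Denominator.** If undosed TEs were kept, 2 affected eyes would be 10.0% of an assumed 20 TEs but 20.0% of 10 dosed TEs. SAP 3.2 keeps an undosed TE out of the regimen columns, so this could affect only the column for all eyes.

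**The case against.** A reader might infer that the SAP leaves the clock entirely open, since time to onset is counted by eye. The documents do not support that. Time to onset is latency, not the flag, and Protocol 9.3.1 and SAP 5.6.1 agree on the subject's first dose. The difficulty is where that rule leads in a by-eye table.

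A reader might also infer that undosed TEs will be in the denominators. SAP 4 leans the other way: sets are determined on each eye, and subject-level sets are built from eye-level ones. What stands is that the either-eye wording sits badly with this and should be tidied.

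Nor can TE time before the Helia dose be called drug-free. Protocol 2.5 allows for remaining exposure in study eyes given 200 µg in the preceding study. Relabelling those events must not make them disappear.

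Other limits also stand:
- No TE-versus-CE comparison, test or decision rule is planned.
- SAP 6 may restrict output to AE overview tables. SAP 5.6 does not title these as treatment-emergent, so the flagged tables by system organ class and preferred term are not certain to appear.
- The listings let a careful reader rebuild the sequence for each eye.
- The table shells are a separate document and were not available. The individual dosing modifications under Protocol 6.1.5 are not visible.
- Protocol 2.3 plans checks soon after each injection. If events cluster there, fewer fall before the TE's own dose than a constant rate implies.

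**Conclusion.** The concern holds as a stated rule with a misleading result. Treatment emergence is anchored to the subject's first dose, by plan the CE dose, while ocular AEs are reported by eye and the TE starts Helia dosing 3 or 9 months later. For a Month-9 TE, the affected share is about 59% of flagged eyes on an assumed 18-month window and 40% on 36 months. These figures rest on an assumed constant rate of 0.5 per eye-year and on assumed cut-offs, so they show scale and do not predict. The arithmetic that needs no rate is that 9 of 18 months, or 9 of 36, of the TE's window precede its own Helia dose.

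An own-eye clock without exposure totals would replace this problem with percentages over unequal eye-time. The point is minor to moderate: it concerns how a primary safety endpoint is labelled and read, and no inference depends on it.

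**What to change.** - **SAP 4:** define the eye-level safety set as eyes that received a Helia dose, and keep the either-eye condition for the subject level only.
- **SAP 5.6 and 5.6.1:** anchor the ocular treatment-emergent flag, including its date imputation, to that eye's first Helia dose, and the non-ocular flag to the subject's first Helia dose. Delete the sham procedure from the definition as clean-up, since Helia is open-label with no placebo.
- **TE tables:** show events between Day 1 and that eye's first Helia dose in a separate row. Do not drop them, because exposure from the preceding study may persist. Footnote this, since eye-time totals alone do not make TE and CE comparable.
- **AE tables:** beside n (%), give total and median eye-years (subject-years for non-ocular AEs) and number of injections per column. A first-event rate per eye-year with an exact 95% interval is optional and descriptive.

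The cost is a few lines of SAP text and a few table rows, from dosing, AE and visit dates already collected. Any rate would assume a roughly constant hazard and be imprecise with about 20 subjects: 6 first events in 12.5 eye-years gives 6/12.5 = 0.48 per eye-year, exact 95% interval 0.18 to 1.04.
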